7.12.3 Index Procedure Visit – Visit 3 (Day 0)

See **Section 6.1** for details of the index procedure and post procedure instructions.

The following assessments/procedures will be performed.

- Handout participant study ID card
- Vital signs prior to discharge
- Concomitant medications
- Assessment of AEs
- Diabetes review and medication titration by treating physician
- Initiate CGM prior to discharge

Participants will be instructed on transitional diet, the importance of hydration, use of CGM for 4 weeks post procedure, and be educated on monitoring hypoglycemic events.

7.12.4 Follow-up Visits

Study follow up visits will be performed at Week 1, 2, 4, and every 4 weeks thereafter. The last study visit is Week 48. The visit windows and assessments/procedures to be performed at each visit are shown in SoA (**Appendix 2**).

To minimize COVID-19 risks, follow up visits may be performed remotely if necessary as below (note: “at home” denotes to participant's home or location). Onsite visit is permitted and will not be considered as a protocol deviation.

- Body weight may be measured at home using the scale provided to participants
- Vital signs and waist circumference may be measured by a visiting nurse at home

- Testing samples (blood, stool, urine) may be collected by a visiting nurse at home
- Assessment of AEs, medication changes, CGM and diabetes review may be performed remotely using site's virtual visit platform
- Lifestyle modification counseling may be performed remotely at each visit.

If situation permits, visits at Week 24 and 48 should be performed onsite. However remote visits at these timepoints will not be considered as protocol deviation.

At Week 48 visit, participants in NIS cohort who received treatment with the Gen 2 device will be consented for participation in long-term follow-up per Appendix 5. Those who consented to long-term follow-up will continue the study per Appendix 5. Those who declined to participate will exit the study. Participants in IS cohort will exit the study after completion of the week 48 visit.

7.12.5 Unscheduled Visits

If a participant is hospitalized, seen in the emergency room, or has an unscheduled clinic visit, efforts should be made to collect the following data:

- Relevant medical history, physical examination, and laboratory test findings
- Concomitant medications
- Assessment of AEs

These assessments should be documented on the eCRFs as appropriate.

7.12.6 Premature Discontinuation

If a participant discontinues the study prematurely prior to his/her 24-week visit, to the extent possible, the participant should be scheduled for an onsite visit (V17A on SoA, Appendix 2), and the following assessments/procedures should be performed.

- Body weight, calculation of BMI, waist circumference
- Vital signs
- Concomitant medications
- Assessment of AEs that occurred since the last visit
- Hematology (CBC)
- Glycemic parameters (FPG, HbA1C, fasting insulin, HOMA-IR, MMTT)
- Comprehensive metabolic panel
- Fasting lipid panel
- Serum iron, transferrin, saturation, ferritin, serum folate, Vitamin D, Vitamin B12
- CGM data
- Diabetes and medication review by treating physician
- Lifestyle modification counseling
- Study exit

If premature discontinuation is decided during a scheduled visit, the visit will be converted to a V17A and assessment procedures should be performed accordingly.

If a participant discontinues the study prematurely after his/her 24-week visit, a remote visit (R17A) should be scheduled. The following tasks will be performed.

- Concomitant medications
- Assessment of AEs that occurred since the last visit
- CGM data, if available
- Study exit

The primary reason for premature study discontinuation must be documented on the eCRF.

8 STUDY AND PARTICIPANT DISCONTINUATION

8.1 Early Study Termination

Sponsor may discontinue the study at any stage for any reason or no reason. Possible reasons for early termination may include unanticipated adverse device effects that may present unreasonable patient risk.

If the study is terminated early, the sponsor will provide a written statement describing why premature termination has occurred, and notify the investigator, Ethic Committee and the regulatory authority (if applicable). All applicable clinical study documents will be subject to the same retention policy as detailed in **Section 13.3**.

8.2 Participant Discontinuation

A participant may withdraw from the study at any time at his/her own request or may be withdrawn at any time at the discretion of the investigator for safety, behavioral, or compliance reasons.

The following events will result in terminating the participant's participation in remaining follow-up:

- Participant voluntary withdrawal
- Participant withdrawn by the investigator as clinically indicated
- Participant becomes pregnant
- Participant lost to follow-up
- Participant death

At the time of discontinuing from the study, if possible, an early discontinuation visit should be conducted. See **Section 7.12.1** for data to be collected at the time of study discontinuation.

The sponsor must be notified of the reason for participant discontinuation. The site will document this information on the electronic case report form (eCRF) and make every effort to give a full description of the reason for withdrawal. Investigator will also report this information to the EC if required per local requirements.

Participants who exit the study early will not be replaced by enrolling additional participants.

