9 SAFETY ASSESSMENT

9.1 Adverse Events

An AE is any untoward medical occurrence in a clinical investigation participant that occurs during any part of the clinical study, whether related to the investigational device or not. Pre-existing conditions are not reported as AEs unless there has been a worsening in severity or frequency which cannot be attributed to the disease's natural history or progression.

For AEs, the event description, severity, date of onset, treatment, outcome, and relationship to device will be collected on the AE eCRF. When reporting an AE, if a clinical diagnosis is available, the diagnosis should be reported instead of individual symptoms.

All procedure- and device-related AEs must be followed until resolution or stabilization (the investigator does not expect any further improvement or worsening of the event).

An Adverse Device Effect (ADE) is any adverse event that is considered possibly-related or related to the device. An ADE may occur at any time after exposure to the investigational device.

Determination of whether there is a reasonable possibility that the investigational device caused or contributed to an AE will be reported by the investigator and reviewed by the medical monitor.

Determination will be based on assessment of temporal relationships, biologic plausibility, association (or lack of association) with underlying disease, and presence (or absence) of more-likely cause.

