9.1.1 Serious Adverse Event

A SAE is an event that:

- Led to a death
- Led to a serious deterioration in health resulting in
 - a life-threatening illness or injury
 - a permanent impairment of a body structure or body function
 - in-patient hospitalization (>24 hours) or prolongation of an existing hospitalization
 - requires medical or surgical intervention to prevent life-threatening illness or injury or permanent impairment of a body structure or body function
- Led to fetal distress, fetal death or a congenital abnormality or birth defect

Here, “life-threatening” refers to an event when the patient is at substantial risk of dying at the time of the adverse event, it does not refer to an event that hypothetically might have caused death if it were more severe; “permanent” is defined as irreversible impairment or damage to a body structure or function, excluding trivial impairment or damage.

For the purpose of this study, diagnostic endoscopy is not considered as “intervention” in the context of SAE. Planned hospitalization for a pre-existing condition is not considered as a SAE.

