For Adverse Event reporting, which includes primary and secondary variables, the primary analysis will be based on Patient counts (e.g., the number and percentage of Patients with events among the total number of Patients). The data will be presented in the format of p% (x/N) [e], with p and x being the percentage and number of Patients with events, respectively, N being the sample size of the analysis population, and e being the total number of events occurred in the x Patients. Asymptotic confidence limits will be presented based on the normal approximation to the binomial distribution for differences in proportions. Exact confidence intervals will be used for all other presentations.

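### Pregnancy or investigator withdrawal ends scheduled follow-up after a single completed procedure, with no active collection of later events, and early leavers with no recorded event count as event-free

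*Protocol*

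**What the plan says.** **Leaving the study.** Protocol Section 8.2 introduces its list with "The following events will result in terminating the participant's participation in remaining follow-up". The list includes "Participant becomes pregnant" and withdrawal by the investigator on clinical grounds. The text above the list says that a participant "may be withdrawn at any time at the discretion of the investigator for safety, behavioral, or compliance reasons". An early discontinuation visit is to be held if possible, and leavers are not replaced.

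**What is still collected.** Section 7.12.6 describes that exit visit: onsite before Week 24, remote afterwards. Both versions include "Assessment of AEs that occurred since the last visit". (Section 8.2 points to 7.12.1 for this content; it is in 7.12.6.) Section 9.1 adds: "All procedure- and device-related AEs must be followed until resolution or stabilization". The same section defines an adverse event as one that occurs while the study is under way.

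**Fetal outcomes.** Section 9.1.1 makes an event serious if it "Led to fetal distress, fetal death or a congenital abnormality or birth defect". SAP Section 4.2 carries a matching data field, AESCONG.

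**Analysis.** The primary endpoint is the ITT proportion with a device- or procedure-related serious adverse event within 12 weeks (Protocol 11.4.2). SAP Section 9 counts events through study day 84. SAP Section 7 reports adverse events as x/N, with "N being the sample size of the analysis population", and SAP 7.3.3 rules out imputation for safety outcomes. The sensitivity analyses in SAP 9.1 repeat the endpoint in the FAS and PP populations.

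**The concern.** The usual reason to take a participant off study is to stop an ongoing study treatment. Here the device treatment is over on Day 0, and a repeat procedure is possible only after 48 weeks (Appendix 5, Section 4.1). A participant who leaves in week 3 has had the full exposure. What ends is the schedule of study tests and, with it, the observation of someone already treated.

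Two things are at stake. First, fetal death and birth defects are named as serious adverse events, yet becoming pregnant triggers exit, and the outcome of a pregnancy normally becomes known long after it is recognised. Second, the primary purpose of this first-in-human study is safety, and the primary endpoint has no rule for a participant whose 12-week status is unknown. Such a participant adds to the denominator and cannot add to the numerator.

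**Working it through.** **Follow-up rules side by side**

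- *Treated, then pregnant or withdrawn by the investigator:* an exit visit if possible (7.12.6) and follow-up of related events already known (9.1). Neither provision reaches an event that begins after exit.
- *Failed endoscopic screening, no energy delivered:* 30 days of safety follow-up (4.1 and 5.4; four weeks in 4.2 and 6.1).
- *Lost to follow-up:* contact attempts continue to the end of the last scheduled visit (8.3).

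So a treated, reachable participant who is withdrawn in week 1 may have less safety follow-up than one who was never treated. Delayed events are plausible on the protocol's own evidence. Section 1.2 reports three duodenal stenoses presenting 2 to 6 weeks after a hydrothermal procedure, and 2.5.2 lists stricture as anticipated with this device, though the technology differs.

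For pregnancy, tests are scheduled at screening, at baseline and before re-treatment only. No supplied section describes pregnancy reporting or an outcome contact.

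**Effect on the primary endpoint**

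The documents give no dropout rate and derive no sample size, so there is no stated figure to reproduce. Inputs:

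- N = 20 (Protocol 11.2; SAP 5.3), 30 (upper figure in Protocol 11.2) and 60 (NIS maximum, Protocol 4.1).
- Observed events x = 0, as an illustration.
- Leavers before day 84 with no related serious event recorded: k = 2. This is an assumption, with k = 1 and 3 shown as the range.

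The SAP specifies exact intervals for single proportions (Section 7). For x events in n:

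- lower limit = Beta quantile (0.025; x, n − x + 1)
- upper limit = Beta quantile (0.975; x + 1, n − x), which for x = 0 is 1 − 0.025^(1/n)

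For N = 20 and k = 2:

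- as planned, 0/20: 1 − 0.025^(1/20) = 16.8%
- leavers excluded, 0/18: 1 − 0.025^(1/18) = 18.5%
- both leavers had an event, 2/20 = 10.0%, interval 1.2% to 31.7%

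| N | k | As planned, upper limit | Leavers excluded, upper limit | All leavers had events |
|---|---|---|---|---|
| 20 | 1 | 16.8% | 17.6% | 5.0% (0.1 to 24.9) |
| 20 | 2 | 16.8% | 18.5% | 10.0% (1.2 to 31.7) |
| 20 | 3 | 16.8% | 19.5% | 15.0% (3.2 to 37.9) |
| 30 | 2 | 11.6% | 12.3% | 6.7% (0.8 to 22.1) |
| 60 | 2 | 6.0% | 6.2% | 3.3% (0.4 to 11.5) |

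The planned result does not change with k. Each such leaver could hide at most 1/N: 5 points at N = 20, 3.3 at 30 and 1.7 at 60. The FAS and PP repeats do not address this, because neither is defined by follow-up to day 84.

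**The case against.** Several stronger readings are tempting, and the documents do not support them.

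- *All follow-up ends.* It does not: Sections 7.12.6 and 9.1 keep an exit assessment and the follow-up of known related events.
- *Fetal events cannot be collected at all.* An event up to the exit visit can be recorded. Serious events are reported when the site learns of them (9.1.3, 9.3.2), and Section 9.1 accepts that a device effect may arise at any time after exposure. What is absent is active collection after exit. Consent pages were removed, so pregnancy wording there cannot be excluded.
- *The safety withdrawals drop out of the numerator.* A participant withdrawn because of a related serious event is already counted. Only one with no such event before exit, and one between exit and day 84, would be misclassified.
- *Pregnancy exits bias the primary endpoint.* Contraception is required, a positive baseline test excludes, and most fetal outcomes would fall after day 84 and would also have to be judged related. The pregnancy gap and the endpoint issue are separate.

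There are also good reasons to stop parts of participation. It includes an endoscopy at weeks 2 to 5, calorie targets, meal tests and stable background medication to Week 24. The size shown above belongs to early exit for any reason, not to this rule alone: voluntary withdrawal and loss to follow-up give the same arithmetic. No hypothesis is tested, withdrawals and their reasons are tabulated (Protocol 11.4.1, SAP 8.1), and Appendix 4 reports no related serious event in the first 27 treated.

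Finally, the supplied SAP names REGENT-1-US, Doc. No. 346, while the protocol is number 196. Whether its x/N rule governs this protocol is unconfirmed. The protocol alone gives an ITT proportion and no rule for incomplete follow-up.

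All of this narrows the point. None of it supplies a route to new events after exit, a pregnancy-outcome contact, or a count of those followed to day 84.

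**Conclusion.** The point holds in limited form. Section 8.2 ends scheduled follow-up of treated participants for reasons that do not require safety observation to end, and the supplied text leaves no active route to later events or to pregnancy outcomes. Sections 8.2 and 9.1.1 do not strictly contradict each other, since one governs participation and the other classifies events; together they leave a gap. Sections 8.2 and 9.1 do need reconciling on how related events are followed after exit.

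On the primary endpoint, with no events in 20 and two assumed early leavers, the upper limit moves from 16.8% to 18.5%. The 10% (1.2% to 31.7%) result is a bound, not an expectation. At N = 60 the move is from 6.0% to 6.2%. The number of leavers is assumed and is not tied to pregnancy or investigator withdrawal, and the x/N rule is taken from a SAP whose application to protocol 196 must be confirmed. This is an inexpensive improvement to safety data in a first-in-human study. It does not invalidate the design.

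**What to change.** **Protocol 8.2.** Separate stopping study tests from ending safety follow-up. Unless consent is withdrawn, participants who become pregnant or are withdrawn by the investigator keep the remote adverse-event contacts already in the Schedule of Activities, at least to day 84 and preferably to Week 48. Add a pregnancy-outcome contact. Reconcile the section with 9.1 and correct the cross-reference to 7.12.6.

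**Analysis plan.** First confirm which SAP applies to protocol 196. In that plan, report how many ITT participants either had a qualifying event or were followed through day 84, and how many leavers are being counted as event-free. Add one sensitivity row giving the primary endpoint on that denominator with an exact interval. Define followed through day 84 by a contact on or after that day, because the Week 12 window of ±7 days allows a visit as early as day 77 (84 − 7).

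**Cost.** A paragraph in an amendment, a few remote contacts, one table row, and possibly a slightly less favourable upper limit.

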8.3 Lost to Follow-up

A participant will be considered lost to follow-up if he or she repeatedly fails to return for scheduled visits and is unable to be contacted by the study site; this term does not apply to missed visits.

The following actions must be taken if a participant fails to return to the clinic for a required study visit:

- The site must attempt to contact the participant and reschedule the missed visit as soon as possible and counsel the participant on the importance of maintaining the assigned visit schedule and ascertain whether or not the participant wishes to and/or should continue in the study.
- Before a participant is deemed lost to follow up, the investigator or designee must make every effort to regain contact with the participant (where possible, 3 telephone or email contacts and, if necessary, a certified letter to the participant's last known mailing address or local equivalent methods). These contact attempts should be documented in the participant's medical record.
- Efforts to regain contact should continue until the end of the participant's last scheduled visit.
- Only if contact with the participant is not regained by the end of the visit window of the last scheduled visit can the participant be considered lost to follow up.

9 SAFETY ASSESSMENT

9.1 Adverse Events

An AE is any untoward medical occurrence in a clinical investigation participant that occurs during any part of the clinical study, whether related to the investigational device or not. Pre-existing conditions are not reported as AEs unless there has been a worsening in severity or frequency which cannot be attributed to the disease's natural history or progression.

For AEs, the event description, severity, date of onset, treatment, outcome, and relationship to device will be collected on the AE eCRF. When reporting an AE, if a clinical diagnosis is available, the diagnosis should be reported instead of individual symptoms.

All procedure- and device-related AEs must be followed until resolution or stabilization (the investigator does not expect any further improvement or worsening of the event).

An Adverse Device Effect (ADE) is any adverse event that is considered possibly-related or related to the device. An ADE may occur at any time after exposure to the investigational device.

Determination of whether there is a reasonable possibility that the investigational device caused or contributed to an AE will be reported by the investigator and reviewed by the medical monitor.

Determination will be based on assessment of temporal relationships, biologic plausibility, association (or lack of association) with underlying disease, and presence (or absence) of more-likely cause.

9.1.1 Serious Adverse Event

A SAE is an event that:

- Led to a death
- Led to a serious deterioration in health resulting in
 - a life-threatening illness or injury
 - a permanent impairment of a body structure or body function
 - in-patient hospitalization (>24 hours) or prolongation of an existing hospitalization
 - requires medical or surgical intervention to prevent life-threatening illness or injury or permanent impairment of a body structure or body function
- Led to fetal distress, fetal death or a congenital abnormality or birth defect

Here, “life-threatening” refers to an event when the patient is at substantial risk of dying at the time of the adverse event, it does not refer to an event that hypothetically might have caused death if it were more severe; “permanent” is defined as irreversible impairment or damage to a body structure or function, excluding trivial impairment or damage.

For the purpose of this study, diagnostic endoscopy is not considered as “intervention” in the context of SAE. Planned hospitalization for a pre-existing condition is not considered as a SAE.

9.1.2 Serious Adverse Device Effect

An SADE is an SAE that is possibly related or related to the device.

9.1.3 Unanticipated Serious Adverse Device Effects

Unanticipated Serious Adverse Device Effects (UADE) are any serious adverse device effect which by its nature, incidence, severity or outcome has not been identified in any of study documents such as the investigational plan, investigator's brochure, Instruction for Use (IFU), or Informed Consent.

When an AE meets the definition of a UADE or that relationship is unknown, the investigator will report the event to sponsor within 24 hours but no later than five (5) working days after the investigator first learns of the effect and reports to the reviewing EC as required.

9.1.4 Abnormal Pancreatic Enzyme Levels

Changes in serum amylase, lipase levels post procedure should trigger assessment for potential pancreatic injury.

The diagnosis of acute pancreatitis requires two of the following three features³:

- Abdominal pain consistent with acute pancreatitis (acute onset of a persistent, severe, epigastric pain often radiating to the back)
- Serum lipase and/or amylase level at least three times greater than the upper normal limit
- characteristic findings of acute pancreatitis on imaging.

For all confirmed events of pancreatitis, the following additional information should be reported if available:

- Signs and symptoms of pancreatitis
- Specific laboratory test supporting a diagnosis of pancreatitis:
- Imaging performed and consistency with pancreatic disease
- Treatment for and complications of the event
- Relevant risk factors for pancreatic disease
- Family history of pancreatitis

9.2 Device Relationship (Causality)

Causality assessment is required for AEs (and SAEs) that occur during clinical investigations. The following terms will be used during this study:

- Related - An AE that is directly and clearly related to the Investigational Device
- Possibly Related - There is a reasonable likelihood that the event is due to the Investigational Device, as evidenced by the following:
 - There may be temporal association with the Investigational Device (e.g., within 24 hours of the DMR procedure)
 - The event, or level of severity of the event, is unlikely to be explained by other etiologies (known to be related to the study disease, patient's baseline medical condition, or concomitant medications)
- Unlikely Related - The AE is not temporally related to the Investigational Device, or is known to be related to one of the following:
 - Morbidity associated with underlying medical condition
 - Anesthesia
 - Upper GI endoscopy
 - Concomitant medication
 - A relationship to the Investigational Device is not biologically plausible
- Not related - The AE is definitely not related to the Investigational Device

